7.2 Collecting, Recording and Reporting of Serious Adverse Events (SAEs) to CIRB

Only related SAEs (definitely/ probably/ possibly) will be reported to CIRB. Related means there is a reasonable possibility that the event may have been caused by participation in the clinical trial. Please refer to the CIRB website for more information on Reporting Requirement and Timeline for Serious Adverse Events.

The investigator is responsible for informing CIRB after first knowledge that the case qualifies for reporting. Follow-up information will be actively sought and submitted as it becomes available.

Related AEs will not be reported to CIRB. However, the investigator is responsible to keep record of such AEs cases at the Study Site File.

7.3 Safety Monitoring Plan

The data and safety monitoring would be performed by the principal investigator and co-investigators. The data would be reviewed monthly or at the point of recruitment of every 10 subjects, whichever occurs first. Data that would be reviewed would include adverse events occurring during the intervention such as excessive patient agitation resulting in injuries or device dislodgements requiring termination of intervention.

15 subjects would be receiving intervention. If 8 or more subjects are unable to meet the composite end-point for completion of intervention, the study would be terminated.

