2.2.1 Potential Risks

The use of VR equipment for an extended period of time may induce a dizzy feeling in older adults. In order to prevent this, we limit the duration of VR usage to under 30 minutes. We will also check in with our participants in regular intervals to assess their comfort levels. Participants with severe visual or hearing impairment will be excluded from this study.

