4.2.2 Study Visits and Procedures

For Virtual Reality Cognitive Training Intervention Group:

- Visit 1 (Week 1): Pre-intervention neuropsychological testing (2 hours)
- Visit 2-11 (Weeks 2-11): Virtual Reality Cognitive Training (50 minutes per session)
- Final Visit (Week 12): Post-intervention neuropsychological testing (2 hours)

For Active Control Group:

- Visit 1 (Week 1): Pre-intervention neuropsychological testing (2 hours)
- Visit 2 & 3 (5 weeks apart): Psychoeducation and Cognitive Stimulation (1 hour per session)
- Final Visit (Week 12): Post-intervention neuropsychological testing (2 hours)

During the VR session and cognitive training, frequent checks will be performed to ensure that subject is comfortable. Should subject express fatigue or discomfort, session can be stopped and resume when subject is able to continue. The number of breaks will be recorded.

Appointment between sessions will be at least 7 days apart.

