8 DATA ANALYSIS

8.1 Data Quality Assurance

Data entered into the electronic databases will be routinely reviewed for the purposes of tracking the progress of the study, assuring accuracy, and completeness of the data. Adverse events or serious adverse events will be recorded and monitored to ensure the safety of the participants.

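### The plan does not settle which adverse events are recorded, over what period or by what enquiry, so events after headset use may be under-captured and counts by arm would not be fairly comparable

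*Combined protocol and SAP*

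**What the plan says.** Three sections of the combined protocol and SAP bear on which adverse events (AEs) are kept.

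- Section 7.1 defines an AE regardless of relatedness, in terms of a pharmaceutical or medicinal product.
- Section 7.2, on reporting to the ethics board (CIRB), says "Related AEs will not be reported to CIRB" and then that "the investigator is responsible to keep record of such AEs cases at the Study Site File". The events meant are the related AEs of the sentence before.
- Section 8.1 carries no such limit: "Adverse events or serious adverse events will be recorded and monitored to ensure the safety of the participants".

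On what is reviewed, 7.3 says "Data that would be reviewed would include adverse events occurring during the intervention" and gives two examples: agitation leading to injury, and device dislodgement that requires the intervention to be terminated.

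On how events come to light, 2.2.1 names dizziness as the risk of the headset and says "We will also check in with our participants in regular intervals to assess their comfort levels". Section 4.2.2 places frequent comfort checks within the VR session and cognitive training. Its visit list gives the virtual reality cognitive training (VRCT) arm ten weekly 50-minute sessions in Weeks 2 to 11. For control it gives "Visit 2 & 3 (5 weeks apart): Psychoeducation and Cognitive Stimulation (1 hour per session", with no week stated for either visit. Both arms are tested at baseline and at Week 12. None of these visits includes a question about AEs since the last contact.

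**The concern.** Dizziness is the one headset risk that the protocol names, and the participants are aged 65 to 85 with mild cognitive impairment. Some of the events that matter most, such as unsteadiness or a fall on the way home, would occur after the session. If no one asks about them, the record depends on a participant remembering the event and volunteering it at a later visit.

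The record itself is also uncertain. A team member following 7.2 could leave an unrelated event off the file, while one following 8.1 would log it. Judging relatedness before recording also makes the count depend on a judgement by staff who know the allocation.

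Finally, the arms have very different numbers of occasions on which a report could be made. A pilot meant to inform a later randomised trial should yield usable tolerability data, and a difference in AE counts by arm could reflect opportunity to report and not event rates.

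**Working it through.** The plan states no AE rate and no power figure to reproduce. The one count that can be checked agrees: up to 30 participants (9.1) in two arms gives 30 / 2 = 15, the number receiving intervention in 7.3.

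**Step 1: which events are recorded.** Under 7.2 the stated filing duty covers related AEs. Under 8.1 it covers AEs and SAEs with no condition on relatedness, arm or timing, and 7.1 defines AEs in the same unconditional way. The sections can be read together, with 7.2 as a reporting rule and 8.1 as the general rule, but the plan does not say so.

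**Step 2: over what period.** The period in 7.3 could mean headset time, the session or the 10-week programme, since 6.1 uses a similar term for the 10 weeks. The examples in 7.3 are in-session events. No AE collection window is stated anywhere.

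**Step 3: by what enquiry.** The visits in 4.2.2 list testing, training, or psychoeducation with stimulation. The checks in 2.2.1 and 4.2.2 concern comfort. Section 4.3.1 acts on complaints that participants make. Section 4.3.2 asks those who withdraw voluntarily about acceptability and feedback. None is an AE enquiry covering the time since last contact.

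**Step 4: contact by arm (4.2.2).**

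| | VRCT | Control | Ratio |
|---|---|---|---|
| All scheduled visits | 1 + 10 + 1 = 12 | 1 + 2 + 1 = 4 | 3.0 |
| Sessions between tests | 10 | 2 | 5.0 |
| Session minutes | 10 x 50 = 500 | 2 x 60 = 120 | 4.2 |

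**Step 5: what this could do to counts (illustration only).** Expected recorded events per arm = n x p x [c + (1 - c) x r]. Here n = 15; p is the true proportion with an event, assumed equal in both arms at 0.20; c is the share of Weeks 2 to 11 with a session (10/10 = 1.0 for VRCT, 2/10 = 0.2 for control); and r is the assumed share of events in weeks without a visit that are reported later.

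- VRCT: 15 x 0.20 x 1.0 = 3.0
- Control, r = 0: 15 x 0.20 x 0.2 = 0.6
- Control, r = 0.5: 15 x 0.20 x (0.2 + 0.4) = 1.8
- Control, r = 1: 15 x 0.20 x 1.0 = 3.0

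With equal true rates the apparent ratio therefore runs from 5.0 through 1.7 to 1.0, depending on r alone. For p from 0.10 to 0.30, VRCT is 1.5 to 4.5, against 0.3 to 0.9 in control with no recall and 0.9 to 2.7 with half recall. The calculation also assumes that every VRCT event is captured at the weekly visit, which the plan does not secure. It shows a possible direction of bias and cannot fix its size.

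**The case against.** A reader might infer that events after the session are excluded by rule and so are missed. The documents do not support that. The wording of 7.3 is inclusive and its examples are illustrations. Section 8.1 is unrestricted. VRCT participants return weekly, both arms attend at Week 12, and 7.4 gives a complaint route to the principal investigator with no limit of time or arm. Headset use is kept under 30 minutes (2.2.1) in a 50-minute session, so at least 20 minutes of each session fall outside it, although the order of components is not stated.

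A reader might also infer that control events would go unrecorded because controls wear no headset. But 7.2 defines related as possibly caused by taking part in the trial, not by the device. By the same test, a fall on the way home after a session could well count as possibly related and would be filed.

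A third tempting inference is a definite multiple by which VRCT events would be over-counted. Any such multiple rests on recall assumptions that the documents do not supply. Moreover, 9.2 plans no comparison of AEs between arms, so no stated analysis is invalidated.

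These objections limit the point to under-capture that may occur and to a comparison that would be unfair if made. They do not remove the difference between 7.2 and 8.1, the undefined period in 7.3, or the absence of any AE enquiry in either arm.

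**Conclusion.** The point holds as a moderate gap in how AEs are ascertained and documented. The plan leaves open which AEs are recorded and over what period, and it relies on spontaneous report for events after the headset is off. Such events may be under-captured. What the documents fix is the imbalance in contact: 10 sessions against 2, and 500 minutes against 120. The resulting bias in counts is not determined by the documents. The conclusion that counts by arm would not be fairly comparable assumes only that more frequent contact gives more opportunity to report.

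**What to change.** 1. Reconcile 7.2 with 8.1 so that every AE in both arms is logged, with relatedness as a recorded attribute and not a condition for recording.
2. Define the period in 7.3, for both arms, as baseline to the Week-12 visit. Baseline is a safer anchor than the first session, because 4.2.2 gives no week for the control sessions.
3. At every scheduled post-baseline visit in both arms (11 in VRCT, 3 in control), put the same short scripted questions: dizziness, nausea, and falls or injuries since last contact. In VRCT, repeat the dizziness question when the headset is removed.
4. Have session staff or another unblinded team member ask, so that the blinded outcome assessor of 4.1 does not learn the allocation. At Week 12 this means someone besides the assessor must be available.
5. Report AEs descriptively by arm and state the unequal number of contacts. Make no between-arm safety claim except over matched enquiry windows, for example the Week-12 enquiry. For that enquiry to be matched, its look-back must have the same length in both arms, because time since last contact can differ.

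The cost is a few minutes per visit and more trivial, unrelated events on file. CIRB reporting does not change, and no contacts are added to the control arm.

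Section 16 already gives results, so new questions may come too late for these participants. In that case, state in the report how AEs were ascertained, and carry the questions into the follow-on protocol.

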7.4 Complaint Handling

Complaints would be informed to the principal investigator and discussed with study co-investigators. Should the complaint be unrelated to the study, the participant's primary physician would be informed. Should the complaint be related to the study involving patient safety and welfare, CIRB would be notified.

8 DATA ANALYSIS

8.1 Data Quality Assurance

Data entered into the electronic databases will be routinely reviewed for the purposes of tracking the progress of the study, assuring accuracy, and completeness of the data. Adverse events or serious adverse events will be recorded and monitored to ensure the safety of the participants.

8.2 Data Entry and Storage

All hardcopy research data will be stored in a cabinet with lock and key access.
All softcopy research data will be stored in a password protected PC.

9 SAMPLE SIZE AND STATISTICAL METHODS

9.1 Determination of Sample Size

As this is a pilot study, there is no power calculation for the sample. Based on the funding available, we intend to recruit up to 30 participants.

9.2 Statistical and Analytical Plans

Intention-to-treat analyses will be performed using the last observation carried forward method for subjects who were lost to follow-up or had missing data. Data will be analysed using IBM SPSS Statistics 26.0. Continuous variables will be presented as mean and standard deviation (SD) or median and interquartile range (IQR) where appropriate, while categorical variables will be presented as frequencies and percentages. A one-way analysis of variance will be conducted to assess the between-group difference of the intervention's effect over time for each outcome measurement. The significance level will be established at $p < 0.05$. Cohen's d effect size (ES) will be reported alongside the p-values, and thresholds of 0.2 for small, 0.5 for moderate, and 0.8 for large effects were employed as guiding benchmarks.

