1 BACKGROUND AND RATIONALE

As a global public health priority, there has been a pressing demand for the development and deployment of novel interventions to prevent and delay the onset of dementia. In recent years, Computerized Cognitive training (CCT) has garnered considerable evidence in improving the cognitive outcomes of individuals living with Mild Cognitive Impairment (MCI), a transitional stage between normal aging and dementia. The aim of this pilot study is to assess the feasibility and efficacy of CCT, specifically a multi-domain Virtual Reality Cognitive Training (VRCT) program on the cognition of individuals with MCI. The VRCT program will be conducted weekly over a period of 10 weeks for participants aged 65-85 with a diagnosis of MCI. 30 participants will be recruited from specialist outpatient clinics and they will be randomized into either the VRCT intervention group or the active control group. All participants will be assessed at baseline and post-intervention. We hypothesize favorable acceptability of the VRCT program. We also postulate positive changes on neuropsychological measures of attention, processing speed, memory and executive function following program completion. We expect these gains in cognition to be translated to improvements on secondary outcomes including mood and self-reported everyday memory functioning. In CGH, there is currently a lack of follow-up intervention options for patients who have received a diagnosis of MCI. Usual care procedures would include medication for risk factors as well as health advice for lifestyle factors such as exercise, diet and cognitively stimulating activities. If outcomes from this study prove to be positive, it will add to the evidence base of the novel application of Virtual Reality technology to Cognitive Training in a clinical setting. Furthermore, this will provide clinicians in CGH with an innovative intervention option to meet the needs of MCI patients in maintaining and enhancing their cognitive functions.

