1.2 Rationale and Justification for the Study

Mild cognitive impairment (MCI) is a symptomatic transitional stage between normal aging and dementia, where individuals display objective evidence of cognitive impairment but still maintain functional and social independence⁵. An estimated 10% to 55% of MCI cases progress into dementia over a 2- to 6-year time period⁶. Given the disability and distress associated with worsening cognition, growing efforts have been made to prevent or delay the progression of MCI to dementia. With an absence of approved pharmacological options to treat the underlying pathophysiological mechanisms of MCI, increasing attention has been placed on lifestyle modifiable factors and non-pharmacological interventions to target the cognitive symptoms⁸.

A non-pharmacological intervention that has garnered interest and considerable evidence in recent years is Computerized Cognitive Training (CCT). CCT involves guided repetitive practice of standardized

tasks designed to target specific cognitive skills or processes, with the aim of improving cognition via reinforcement of neural pathways⁹. Accessibility to cognitive training is enhanced with the use of technology, particularly for older adults whose mobility may be limited. The computerized features also enable a more individualized approach where activities may be tailored to the users' ability levels, thereby improving user engagement. The efficacy of CCT has been rigorously reviewed in recent meta-analyses of randomized control trials which reported cognitive benefits in both cognitively healthy older adults and patients with mild cognitive impairment^{10,11}. Notably, the overall effect size of CCT on cognition was found to be higher for individuals with MCI ($g = 0.35$) as compared to individuals with dementia ($g = 0.28$)¹¹ as well as healthy older adults ($g = 0.22$)¹⁰, indicating the use of CCT as a viable intervention for enhancing cognition in people with MCI.

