1.2.1 Rationale for the Study Purpose

Among the various types of CCT interfaces that are currently available, including computer/tablet-based programs and videogames, Virtual Reality (VR) technology is the most recent and novel application of CCT. As compared to its traditional counterparts, the wrap-around display screens of VR systems offer the added advantage of a simulating and immersive environment that produces a sensation of "presence" or "being there". VR systems also afford a versatile experimental platform that can provide timely feedback to clinicians regarding patient progress via real-time monitoring of the system performance¹². Evidence for the efficacy of VR on health-related outcomes has been demonstrated in other clinical populations including cognitive rehabilitation for patients of traumatic brain injury¹³ and exposure therapy for patients with anxiety and phobic disorders¹⁴. While the evidence base for VR application on MCI patients is currently still limited, available research suggests its utility in enhancing treatment adherence and cognitive outcomes of MCI patients. In a study examining the effects of an attentional task on selective and sustained attention, participants with MCI were exposed to two task conditions – a highly realistic image-based rendered VR condition and a paper version of the task. Not only did participants endorse a preference for the VR interface over the paper condition, apathetic participants reported greater preference for the VR condition than non-apathetic participants, indicating VR's potential in improving adherence to cognitive training¹⁵. One study had developed a 6 months VR memory training (inclusive of 3 months training phase and 3 months booster phase) for nursing home residents with memory deficits¹⁶. The authors found significant improvement in memory test scores, especially in long-term recall, for participants in the intervention group whereas those in the control group demonstrated progressive decline in their memory functions¹⁶. These positive results in the memory domain are supported by another study which examined the efficacy of memory and balance training VR program on participants with MCI¹⁷. Finally, even among MCI participants of Chinese ethnicity, VR seems to be acceptable and efficacious, with the VR group showing greater improvement in objective memory performance post-training than the non-VR group¹⁸.

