2.1 Primary Objectives

Our primary objective is to (1): assess the retention and adherence rates of the VRCT intervention and (2) examine effects of VRCT on cognition, everyday memory performance and mood of older adults with MCI.

2.2 Potential Risks and Benefits:

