4.3.2 Discontinuation Visit and Procedures

If voluntary withdrawal occurs, participant will be asked to complete the self-report questionnaire to assess intervention acceptability and to collect feedback on the program.

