6.3 Concomitant therapy

Participants assigned to the active control group will undergo two hourly sessions of psychoeducation on cognitive health and cognitive stimulation activities. They will also be given a cognitive stimulation kit consisting of puzzles and games and provided with a weekly guide to engage in these intellectual activities weekly at home.

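### With outcomes scored only at weeks 1 and 12, LOCF carries the baseline forward and enters zero change for anyone without a week-12 score

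*Combined protocol and SAP*

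**What the plan says.** Section 9.2 sets the missing-data rule: "Intention-to-treat analyses will be performed using the last observation carried forward method for subjects who were lost to follow-up or had missing data". It then plans a one-way analysis of variance of the between-group difference over time for each outcome, reported with p-values and Cohen's d. It plans no other missing-data method and no sensitivity analysis.

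Section 1 gives the assessment schedule: "All participants will be assessed at baseline and post-intervention". Section 4.2.2 agrees. In both arms neuropsychological testing takes place at week 1 and week 12, and the visits between are for training or psychoeducation only. On voluntary withdrawal, section 4.3.2 says the "participant will be asked to complete the self-report questionnaire to assess intervention acceptability and to collect feedback on the program"; no cognitive, mood or everyday-memory score is listed there.

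Section 3.5 includes those who finish eight or more of the ten VRCT sessions and does not replace dropouts. Section 2.1 makes it a primary objective to "examine effects of VRCT on cognition, everyday memory performance and mood of older adults with MCI".

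**The concern.** With two time points there is no intermediate score to carry forward. LOCF becomes baseline carried forward: each participant without a week-12 score is treated as having been measured and found not to have changed. Participants who stop training but attend week 12 are unaffected.

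This is often defended as conservative, but that holds only if controls do not change on average or if equal shares are missing in both arms. The documents support neither. Controls receive two sessions, and section 6.3 adds: "They will also be given a cognitive stimulation kit consisting of puzzles and games and provided with a weekly guide". Section 1.2.1 cites a memory-training study in which the trained group improved, "whereas those in the control group demonstrated progressive decline in their memory functions". So control change could go either way. Unequal missingness is also plausible: VRCT has ten sessions against two, and the discontinuation rule in section 4.3.1 concerns VR discomfort, which only the VRCT arm can experience.

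At stake is the efficacy part of the primary objective. The difference and Cohen's d would depend on who missed week 12 as well as on training, and section 1.2.1 intends the pilot to guide a later randomised trial. Retention and adherence, also primary, are not affected.

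**Working it through.** **Inputs from the documents.** Up to 30 participants (section 9.1), 15 receiving the intervention (section 7.3); two outcome assessments (sections 1 and 4.2.2). Section 1.2 says "Notably, the overall effect size of CCT on cognition was found to be higher for individuals with MCI", with g = 0.35. Section 9.2 takes 0.80 as a large effect. The documents give no power calculation, dropout rate, SD or drift, so there is no figure in the plan to reproduce. The limit of 8 in section 7.3 is a stopping threshold for completing the intervention, not an expected number of missing scores, and is not used.

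**Assumptions.** 15 per arm, SD 1 at each time point, pre–post correlation 0.7, higher scores better, 0.35 read in baseline SDs, and the one-way ANOVA read as a two-group test of change. Missing counts and drift are illustrative.

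**Formula.** Let D be the true difference in mean change. With missingness unrelated to outcome:

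E[LOCF difference] = (1 − mV)(drift + D) − (1 − mC) × drift = (1 − mV) × D − (mV − mC) × drift

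Example, 5 VRCT and 1 control missing, D = 0.35, drift +0.3: (10/15)(0.35) − (4/15)(0.3) = 0.233 − 0.080 = 0.153.

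| True D | Missing, VRCT v control | Drift −0.3 | Drift 0 | Drift +0.3 |
|---|---|---|---|---|
| 0.35 | 5 v 1 | 0.313 | 0.233 | 0.153 |
| 0.35 | 3 v 1 | 0.320 | 0.280 | 0.240 |
| 0.35 | 3 v 3 | 0.280 | 0.280 | 0.280 |
| 0.35 | 1 v 1 | 0.327 | 0.327 | 0.327 |
| 0.35 | 1 v 5 | 0.247 | 0.327 | 0.407 |
| 0.80 | 5 v 1 | 0.613 | 0.533 | 0.453 |
| 0 | 5 v 1 | +0.080 | 0 | −0.080 |

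All four directions occur. Most rows shrink the effect. The 1 v 5 row at drift +0.3 inflates it. The last row creates a difference where none exists. At 3 v 0 with drift −0.35 the effect is unchanged: 0.8 × 0.35 + 0.2 × 0.35 = 0.35.

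**Coverage** (40,000 simulated trials per scenario; simulated means match the formula within 0.004). The LOCF 95% interval covers the true 0.35 at 5 v 1 in 95%, 93% and 89% of trials for drift −0.3, 0 and +0.3. For true 0.80 the figures are 90%, 85% and about 80%. At 1 v 1 coverage is 95%. With no true effect and drift ±0.3 at 5 v 1, type I error is about 6%. ANCOVA of observed scores averages 0.35 or 0.80 with 95% coverage throughout.

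**If dropout depends on outcome.** The LOCF bias is mC × (mean change of missing controls) − mV × (mean change of missing VRCT participants). With true 0.35, no drift, 5 v 1 missing and dropout favouring poor change:

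| Dropout selected in | ANCOVA mean (coverage) | LOCF mean (coverage) |
|---|---|---|
| Both arms | 0.54 (89%) | 0.36 (95%) |
| VRCT only | 0.59 (87%) | 0.42 (95%) |

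**Shifted multiple imputation** (4,000 trials, 20 imputations each, same 5 v 1 setting). Mean estimate after lowering imputed VRCT scores:

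| Dropout | Shift 0 | 0.25 SD | 0.5 SD | 0.75 SD |
|---|---|---|---|---|
| Selected in both arms | 0.55 | 0.47 | 0.38 | 0.30 |
| Selected in VRCT only | 0.59 | 0.51 | 0.43 | 0.34 |
| Random | 0.36 | 0.27 | 0.19 | 0.11 |

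No single shift recovers 0.35 in all three cases, so the whole range has to be shown.

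**The case against.** The strongest reply is that the size is unknown and the remedy is not clearly better in an unpowered pilot.

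- **Size.** Every missing count and drift above is assumed, and section 16 gives no missing counts. This stands: the harm is small at 1 v 1 and nil with complete data.
- **Direction.** The inflation example needs more missing controls, against what the design suggests. At 5 v 1 and D = 0.35, inflation needs drift below −(5/15)(0.35)/(4/15) = −0.44 SD. The cited decline was in nursing-home residents in a 6-month programme, not outpatients over 12 weeks. This stands too: shrinkage is the likelier result, and the created difference of 0.08 barely moves type I error.
- **Cohen's d.** The entered zeros also reduce the SD of change, so d falls less than the raw difference. Taking d on the pooled SD of change (section 9.2 does not define it), its mean is 0.47 with nothing missing. At 5 v 1 it is 0.47, 0.34 and 0.21 for drift −0.3, 0 and +0.3. The offset is real but not dependable.
- **Precision.** At true 0.35 with random dropout and no drift, root mean squared error is lower for LOCF than for ANCOVA: 0.278 v 0.302 at 5 v 1, and 0.261 v 0.297 at 3 v 3. ANCOVA is better at 5 v 1 with drift +0.3 (0.304 v 0.321) and clearly better at true 0.80. LOCF's gain comes from pulling estimates towards zero change, which is a poor basis for planning a trial.
- **Selective dropout.** If poor responders leave, ANCOVA overstates the effect more than LOCF does. This stands, and it is why a sensitivity range is needed rather than a simple swap of methods.

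**Conclusion.** The concern holds and should be fixed. That LOCF enters exactly zero change for a participant with a baseline but no week-12 score follows directly from the assessment schedule. Confidence in that mechanism is high; confidence in its size in this trial is low, because it depends on missing counts, drift and SD that the documents do not give. On the illustrative assumptions, a true 0.35 SD becomes 0.15 to 0.31 at 5 v 1 missing, and 0.33 at 1 v 1. The bias affects the cognition, everyday-memory and mood part of the primary objective only.

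A related conflict leaves unclear who LOCF applies to: the session-completion rule in section 3.5 operates in one arm only and contradicts the intention-to-treat label in section 9.2.

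**What to change.** In section 9.2:

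1. Make ANCOVA of observed week-12 scores on arm and baseline score the main analysis. Include everyone with a week-12 score, in the assigned arm, whatever the number of sessions attended. State that it assumes missingness at random given arm and baseline.
2. Report the number of missing week-12 scores by arm. This is the minimum step and shows whether the problem arose at all.
3. Add a sensitivity analysis by multiple imputation within arm from baseline score. Add the proportion of scheduled sessions attended (ten VRCT, two control) only if there are enough observed scores. Shift imputed scores in the unfavourable direction by 0, 0.25, 0.5 and 0.75 SD, in each arm separately, and report the whole range. That range is a judgement, not a figure from the documents.
4. Keep LOCF, if at all, as a labelled sensitivity analysis.

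In section 3.5, reconcile the eight-of-ten-session rule with intention to treat, so that VRCT participants are not dropped by a rule that controls do not face.

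The cost is one paragraph of section 9.2, one line of section 3.5 and a re-analysis of data already collected, labelled post hoc because section 16 already reports results. Intervals are wider: mean width 1.24 against 1.04 SD at 5 v 1, and 1.12 against 1.11 at 1 v 1. That comparison also includes the move from change scores to ANCOVA.
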